The single entity fit-for-purpose capsule formulation of RZR shows a moderate negative food effect, with a 50% decrease in C_{24hr} when co-administered with a high-fat meal. As such, in this study, subjects will be instructed to take study drugs on an empty stomach after an overnight fast, at least 1 hour before the morning meal. Drugs should be taken with water, but without food. A drug-drug interaction study with MK-3682 and RZR (MK-3682 PN008) showed no clinically significant drug interactions, thus supporting the coadministration of these drugs without need for dose adjustment.

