5.2.2 Timing of Dose Administration

MK-3682 and RZR

All doses of MK-3682 and RZR should be taken on an empty stomach after an overnight fast, at least 1 hour before the morning meal. Study medications should be taken with water but without food. In addition, subjects should fast overnight prior to reporting to the study site for dosing on Treatment Day 1 (Visit 2) and for all other visits at which a pre-dose PK sample is to be collected. For study visits after Visit 2, if there are cases in which a morning visit is not feasible and a subject is seen in the afternoon, the subject should take their study medication in the morning, after an overnight fast, as per their regular schedule and PK samples will still be collected during these visits.

If a subject misses a dose of MK-3682 or RZR and it is less than 8 hours before the next dose, the missed dose should be skipped and the normal dosing schedule resumed. Subjects should not double the next dose in order to compensate for what has been missed.

If a subject misses a dose of MK-3682 or RZR and it is greater than 8 hours before the next dose, the missed dose should be taken at least 2 hours after last meal and 1 hour before next meal and the normal dosing schedule resumed.

If for any reason MK-3682 or RZR needs to be interrupted, the entire regimen should be interrupted and can be interrupted for up to 3 days. If the interruption lasts for more than 3 days, consult the Sponsor Protocol team.

Ribavirin

Dosing of RBV should follow the approved local prescribing information.

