7.1.3.2.1 Pharmacokinetics: Blood Collection for Plasma MK-3682 (and Metabolites), and Ruzasvir

Sample collection, storage and shipment instructions for plasma samples will be provided in the operations/laboratory manual.

Sample Collection

Pharmacokinetic samples will be collected from all enrolled subjects according to the PK sampling schemes shown in [Table 13](#).

- Subjects in the Intensive PK/PD Group will be providing additional PK samples on Day 3 (pre-dose) and on Day 7 (post-dose) that are not being collected from the other subjects in the study.

Dosing and Sample Collection Instructions

- As specified previously in Section 5.2.2, Timing of Dose Administration, all doses of MK-3682 and RZR should be taken on an empty stomach after an overnight fast, at least 1 hour before the morning meal, with water but without food.
- On all PK visits where a pre-dose sample will be collected, the visit should occur prior to the subject's regular time for taking their study medication and the subject should withhold their dose until after the visit.
- For pre-dose PK visits after Visit 2 (Day 1), if this visit time is not feasible, the subject should be instructed to take their study medication as per their regular schedule. PK samples should still be collected during the visit.

Note: While every effort should be made to schedule visits with PK draws so that they occur within the window specified in [Table 13](#); when this is not possible, the PK samples should still be collected even if out of window.

- The date and time of each PK sample as well as the date and time of the last dose of MK-3682 and RZR prior to the PK sample will be recorded.

Recording and Entering Meal Information

- Subjects will be provided with a meal diary with instructions for recording meal data that includes what they eat/drink and the time of the meal. Subjects should record ALL meal data from 48 hours BEFORE the PK visit through the day of the PK visit.
- The site will be responsible for entering the appropriate data from the meal diary, as well as the qualitative fat content of the meal, in the eCRF according to the eCRF Entry Guidelines. Meal data should be entered by the site as follows:
 - For visits where only a predose PK sample is collected, enter meal data for up to **5 hours before, and up to 2 hours after** the MK-3682 and RZR dose administered on the day **prior** to the predose PK visit.

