 - For visits where a postdose PK sample is also collected, also enter meal data for up to **5 hours before, and up to 2 hours after** the MK-3682 and RZR dose administered at the study site.
 - For subjects who may take multiple meals during the time window, only the meal closest to the last dose prior to the PK samples will be entered.

Table 13 Pharmacokinetic and Pharmacodynamic Sampling Time Points

Visit Number	Study Day/Week	Time Relative to Dose of MK-3682/RZR ^{1,2}	All Subjects	Intensive PK/PD Group Subjects	
			PK Time Points for MK-3682 and RZR	PK Time Points for MK-3682 and RZR	PD (Viral Kinetic) Time Points
2	Day 1	Predose	X	X	X
2-3	Day 1 – Day 2	2, 4, 8, 12, 24, and 32 hours postdose	n/a	n/a	X
4	Day 3	Predose	n/a	X ³	X
5	Day 5	n/a	n/a	n/a	X
6	Day 7	Predose	X	X ³	X
		0.5-, 2-, and 4-hour postdose	n/a	X ³	n/a
7	Week 2	Predose	X	X	n/a
8	Week 4	Predose	X	X	n/a
		0.5- and 2-hour postdose	X	X	n/a
9	Week 6	Predose	X	X	n/a
10	Week 8	Predose	X	X	n/a
12	Week 12	Predose	X	X	n/a
14	Week 16 ⁴	Predose	X	X	n/a
21	HCV/HIV Viral Failure Confirmation Visit ⁵	n/a	X ⁵	X	n/a
22	Early Discontinuation Visit ⁵	n/a	X ⁵	X	n/a

ECG = electrocardiogram; HCV = hepatitis C virus; HIV = human immunodeficiency virus; n/a = not applicable; PD = pharmacodynamic(s); PK = pharmacokinetic(s); RZR = ruzasvir.

¹ Time relative to last dose of MK-3682 and RZR must be recorded in the electronic case report form.

² After study Visit 2, if there are cases in which a morning visit is not feasible and a subject is seen in the afternoon, the subject should take their study medication in the morning, after an overnight fast, as per their regular schedule (in accordance with Section 5.2.2 Timing of Dose Administration) and PK samples will still be collected during these visits.

³ ECGs will be collected on ALL subjects on screening, Day 1, TW2, TW4, TW8, TW12, FW4 and FW12; Additional ECGs will be collected on subjects in the Intensive PK/PD Group subjects on Day 3 and Day 7.

⁴ Week 16 only applies for those subjects whose treatment duration may be extended. **PK sampling scheme for these subjects remain the same with the addition of TW16 time point.**

⁵ PK samples and meal information for PK are to be collected at HCV/HIV viral confirmation or early discontinuation visits that occur only during the study treatment period.

Note: Approximately 4 mL of blood will be collected at each specified time point for plasma PK assessment of MK-3682 (and metabolites).

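### Two gaps in the PK meal-entry rules: no consistent anchor dose when the sample follows a same-day home dose, and a one-meal limit that can drop a meal eaten 1 to 5 hours before dosing

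*Combined protocol and SAP*

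**What the plan says.** **Meal entry (7.1.3.2.1, Recording and Entering Meal Information).** Subjects keep a diary of all meals from 48 hours before the PK visit through the visit day. The site transfers part of it to the eCRF, with the qualitative fat content:

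- The window runs from up to "5 hours before, and up to 2 hours after" a dose.
- At visits with only a pre-dose sample, that dose is "the MK-3682 and RZR dose administered on the day" before the visit.
- At visits that also have a post-dose sample, the window is also applied to "the MK-3682 and RZR dose administered at the study site".
- One meal per window is kept: "For subjects who may take multiple meals during the time window, only the meal closest to the last dose prior to the PK samples" goes into the eCRF.

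Entry also follows eCRF Entry Guidelines, which are not among the documents.

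**Dosing (5.2.2).** Study drug "should be taken on an empty stomach after an overnight fast, at least 1 hour before the morning meal". A missed dose with more than 8 hours to the next may be taken late, separated from the previous meal by at least 2 hours and from the next by at least 1 hour.

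**Afternoon visits (7.1.3.2.1, 5.2.2, Table 13 footnote 2).** Pre-dose PK visits later than the first dosing day have an exception: "if this visit time is not feasible, the subject should be instructed to take their study medication as per their regular schedule". Sampling goes ahead all the same.

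**Use of the data (4.2.4.2, 4.2.5.3, 8.4.1.2).** Trough concentration is the primary PK endpoint, and the samples feed PK-safety and PK-efficacy modelling. The RZR capsule "shows a moderate negative food effect, with a 50% decrease in" C24hr when given with a high-fat meal.

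**The concern.** RZR exposure depends on food, so the meal record is the covariate that lets an analyst separate a food effect from other causes of a low concentration. It works only if it describes the dose that produced the sample and shows whether that dose was taken fasted.

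The rules can fail on both counts, by separate routes. At an afternoon visit they can attach the record to a dose taken a day before the relevant one. And where a subject ate some hours before a dose and again soon after it, the eCRF may show only the later, permitted meal.

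In either case a fed dose could look fasted in the analysis dataset, and its effect would pass as unexplained variation in exposure. That matters most for the PK-efficacy and PK-safety relationships named in 2.1, and for the RZR dose-response question that 4.2.4.2 gives as a reason for the trial.

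**Working it through.** The plan gives no figure to reproduce. The check sets the rules side by side and does interval arithmetic on their own times.

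**A. Which dose anchors the window at an afternoon visit?**

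| Rule in 7.1.3.2.1 | Dose it points to |
|---|---|
| Visits with a pre-dose sample only | Previous day's dose |
| Visits that also have a post-dose sample | Also the dose given at the site |
| Several meals in the window | Last dose before the sample: that morning's home dose |

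No window rule covers the same-day home dose, and the first and third rules point to different doses.

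Let D be the usual dosing time, the same on both days.

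- Window around the previous day's dose: D − 24 − 5 to D − 24 + 2, that is D − 29 h to D − 22 h.
- Window around the same-day dose: D − 5 h to D + 2 h.
- Gap: (D − 5) − (D − 22) = 17 h, so the overlap is zero for any D.

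Assuming doses between 06:00 and 09:00 and visits between 13:00 and 16:00, the sample falls 13 − 9 = 4 h to 16 − 6 = 10 h after the last dose, and 28 to 34 h after the previous day's dose.

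Scope, counted from Table 13 after Day 1 for the 12-week regimen: main-group subjects have PK visits at Day 7 and Weeks 2, 4, 6, 8 and 12. Five of these six have only a pre-dose sample (all but Week 4). At an afternoon Week 4 visit the post-dose rule refers to a dose given on site, so a home dose is not covered there either. The viral-failure confirmation and early-discontinuation visits also require meal information during treatment. Table 13 gives them no time relative to dose, so neither window rule plainly applies.

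**B. When does the one-meal limit drop a pre-dose meal?**

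Let b be the hours from the dose to the next meal and m the hours from the previous meal to the dose. To be both permitted and in the window, b must lie between 1 and 2; to be in the window, m must be at most 5. The nearer meal is kept, so the pre-dose meal is dropped only if m > b. The share of the 5-hour pre-dose window affected is (5 − b)/5. The part lying less than 2 h before the dose, the separation that 5.2.2 accepts for a late missed dose, is (2 − b)/5.

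| b | Pre-dose meals dropped | Share of window | Part less than 2 h before dose |
|---|---|---|---|
| 1 h | more than 1 h before | 4/5 = 80% | 1/5 = 20% |
| 1.5 h | more than 1.5 h before | 3.5/5 = 70% | 0.5/5 = 10% |
| 2 h | more than 2 h before | 3/5 = 60% | 0 |
| over 2 h | none (outside window) | 0 | 0 |

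A meal less than 1 h before the dose always has m < b and is always kept over a permitted breakfast.

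For an ordinary morning dose, a drop requires a broken overnight fast. For a late missed dose it does not: a meal 2 to 5 h before is allowed, and with the next meal at 1 to 2 h after, m > b throughout, apart from a tie when both are exactly 2 h. In that case every permitted pre-dose meal in the window is dropped.

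**The case against.** The strongest case on the other side has five parts.

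- **The rule keeps the meal most likely to matter.** The 50% figure in 4.2.4.2 is for a high-fat meal taken with the dose. The meal nearest to that condition is always kept, and the documents give no effect size for a meal 1 to 5 hours earlier. This stands. A reader might infer that a permitted breakfast routinely hides a halving of RZR trough; the documents do not support that.
- **The 60% to 80% are shares of clock time**, not of samples, subjects or fasting breaches. This stands. How often subjects eat before dosing is not given.
- **Afternoon records need not be wrong.** A reader might infer that every afternoon visit records meals around the wrong dose. That follows only if the site applies the previous-day rule; the several-meals rule points to the right dose. What the text shows is a conflict, and sites may resolve it differently.
- **Afternoon samples are not troughs.** On the assumed times they fall 4 to 10 h after dosing, so the anchor gap bears on the modelling data rather than on the primary PK endpoint. Sample and last-dose times are recorded, so these samples can be identified. Adherence has its own check, the medication diary against unused drug (7.1.1.8).
- **Other documents may settle it.** The eCRF Entry Guidelines could name the anchor dose, 8.6.3 leaves PK analyses to the supplemental SAP, and the diary holds all meals at source. This limits the harm, but a guideline outside the protocol does not remove the contradiction within it.

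A reader might also take the two defects as one causal chain. They are independent: the anchor gap has nothing to do with one meal displacing another.

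**Conclusion.** Both defects are present in the text of 7.1.3.2.1, and both are minor. At afternoon visits after a same-morning home dose, two entry rules point to doses a day apart, with windows 17 hours apart, and no window rule covers the home dose. Separately, the one-meal limit can drop a meal eaten 1 to 5 hours before the dose when a permitted meal at 1 to 2 hours after it is closer. This includes meals that 5.2.2 allows before a late missed dose.

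The size of any bias cannot be stated. The documents give neither the frequency of afternoon visits or pre-dose meals nor a food effect for meals that are not taken with the dose. The gap assumes the same dosing time on both days; the 4-to-10-hour sampling interval rests on the assumed clock times above.

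The consequence is limited to interpreting drug concentrations and to PK-efficacy and PK-safety modelling. The SVR12 analysis is unaffected.

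**What to change.** Replace the three entry bullets with one rule: for each PK sample, enter every meal, with its time and qualitative fat content, from 5 hours before to 2 hours after the recorded last dose taken before that sample, whether that dose was taken the same day or the day before, at home or on site. Apply it also to the viral-failure confirmation and early-discontinuation visits. The Day 1 pre-dose sample has no preceding dose and needs no entry. Derive a fed/fasted flag from the pre-dose meals, define it in the supplemental SAP, and align the eCRF Entry Guidelines.

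The cost is a few more eCRF lines per PK visit. The last-dose date and time are already recorded. The 48-hour diary covers the whole window whenever the last dose was within 48 − 5 = 43 hours of the visit, so neither the morning nor the afternoon schedule needs a new procedure. Visits already entered under the present rules can be completed from the diaries.

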7.1.3.2.2 Pharmacodynamics: Viral Kinetics

HCV RNA samples also will be collected at the Week 1, 2, 4, 6, 8, 10 and 12 visits for all subjects during treatment (and Week 14 and 16 visits for subjects whose treatment duration may be extended). Additional samples for HCV RNA will be collected on a subset of subjects in the Intensive PK/PD group (see [Table 13](#)). The data from this sub-study will be used to validate the existing viral dynamics model for MK-3682 and RZR. A total of approximately 30 subjects, the first 5 subjects for each GT1-6 who consent to participate, will undergo additional PK and PD evaluations and have electrocardiographs (ECGs) performed.

See Section 6.0 Trial Flow Chart and [Table 13](#) for detailed information on sample collection and visits.

7.1.3.3 HCV Evaluation

The following specimens are to be obtained for HCV evaluation as part of efficacy/pharmacogenetic measurements:

- Samples for HCV GT evaluation must be obtained for inclusion in the study. All baseline samples will be genotyped using the FDA-approved Abbot HCV Real Time Genotype II assay that detects HCV GTs 1a, 1b, 2, 3, 4, 5, and 6 through the use of GT-specific fluorescent-labeled oligonucleotide probes in a real-time reverse transcription polymerase chain reaction (RT-PCR) assay. The RT-PCR reaction uses 3 sets of HCV-specific amplification primers targeting the 5' untranslated region (UTR) (for all GTs) and NS5B regions from GT1a and 1b. The assay has accuracy of >96% for GT1, 1a, 1b, 2, 3, and 5; 89% for GT5, and 83% for GT6; with 100% specificity in HCV serologically negative plasma samples.
- Blood must be drawn from each subject to assess HCV RNA plasma levels at various time points as shown in the Trial Flow Chart (Section 6.0). HCV RNA in plasma will be measured using a COBAS™ AmpliPrep/COBAS™ Taqman HCV Test, version 2.0® assay with an LLOQ of 15 IU/mL. Leftover plasma may be used for viral resistance testing if needed. Also, leftover plasma may be used for FBR only if the subject signed for FBR consent.
- Blood must be drawn from each subject to assess viral resistance mutation and processed as instructed by the central laboratory manual. Leftover plasma may be used for FBR only if the subject signed for FBR consent.
- Protein and metabolites may be measured from blood samples to compare biomarkers measured prior to treatment to biomarkers measured at several time points during treatment that correlate with subject response to treatment (e.g., sustained viral response).
- Samples collected for genetic analysis are obtained at Day 1. Any leftover DNA may be used for FBR only if the subject signs for FBR consent.

NOTE: Samples may also be used for future assay development and validation if the subject signed for FBR consent.

7.1.3.4 HIV Evaluation

The following specimens are to be obtained for HIV evaluation:

- Blood must be drawn from each subject to assess HIV RNA plasma levels at screening as shown in the Trial Flow Chart (Section 6.0). HIV RNA in plasma will be measured using a COBAS™ AmpliPrep/COBAS™ TaqMan HIV-1 Test, version 2.0® assay with a LLOQ of 20 IU/mL.
- Blood must be drawn from each subject with HIV co-infection to assess immunologic status. CD4+ T-cell counts will be obtained at screening as shown in the Trial Flow Chart (Section 6.0).
- In the event of HIV virologic breakthrough, a sample for HIV viral resistance is to be collected at the viral failure confirmation visit.

The following nomenclature will be used when describing HIV RNA levels:

- HIV-1 RNA <LLOQ, TND
- HIV-1 RNA <LLOQ, Target Detected
- HIV-1 RNA IU/mL

7.1.3.5 HBV Evaluation

- Blood must be drawn from each subject to assess HBsAg, anti-HBc, and anti-HBs at screening.
- For subjects who are anti-HBc positive, HBV DNA will be assessed at screening, and both HBV DNA and HBsAg will be monitored during the trial. The results of these assessments will be used to determine HBV reactivation, which will be reported as an Event of Clinical Interest as specified in Section 7.2.3.2.
- Subjects who develop HBV reactivation will be managed by site investigators according to current treatment guidelines and/or local standard of care.
- Subjects who develop HBV reactivation may continue in the trial at the discretion of the site investigators.

7.1.3.6 Planned Genetic Analysis Sample Collection

Sample collection, storage and shipment instructions for Planned Genetic Analysis samples will be provided in the laboratory manual.

7.1.3.7 Future Biomedical Research Samples

The following specimens are to be obtained as part of Future Biomedical Research:

- DNA for future research
- Leftover main study plasma from HCV RNA stored for future research
- Leftover main study plasma from viral resistance and biomarkers stored for future research

7.1.4 Other Procedures

7.1.4.1 Withdrawal/Discontinuation

Subjects who discontinue treatment prior to completion of the treatment regimen should be encouraged to continue to be followed for all remaining study visits.

When a subject discontinues/withdraws from participation in the trial, all applicable activities scheduled for the final trial visit should be performed at the time of discontinuation. Any adverse events which are present at the time of discontinuation/withdrawal should be followed in accordance with the safety requirements outlined in Section 7.2 - Assessing and Recording Adverse Events.

7.1.4.1.1 Withdrawal From Future Biomedical Research

Subjects may withdraw their consent for Future Biomedical Research. Subjects may withdraw consent at any time by contacting the principal investigator for the main trial. If medical records for the main trial are still available, the investigator will contact the Sponsor using the designated mailbox ([contact]). Subsequently, the subject's consent for Future Biomedical Research will be withdrawn. A letter will be sent from the Sponsor to the investigator confirming the withdrawal. It is the responsibility of the investigator to inform the subject of completion of withdrawal. Any analyses in progress at the time of request for withdrawal or already performed prior to the request being received by the Sponsor will continue to be used as part of the overall research trial data and results. No new analyses would be generated after the request is received.

In the event that the medical records for the main trial are no longer available (e.g., if the investigator is no longer required by regulatory authorities to retain the main trial records) or the specimens have been completely anonymized, there will no longer be a link between the subject's personal information and their specimens. In this situation, the request for specimen withdrawal cannot be processed.

7.1.4.2 Subject Blinding/Unblinding

This is an open label trial; there is no blinding for this trial.

7.1.4.3 Domiciling

The subjects who are participating in the Intensive PK/PD group will report to the clinical research unit (CRU) on the morning of Day 1 prior to trial drug administration and will remain either in the unit or in a local facility until completion of the 32-hour blood draw after the first dose of study medication. At the discretion of the investigator, subjects may be requested to remain in the CRU longer.

7.1.4.4 Calibration of Critical Equipment

The investigator or qualified designee has the responsibility to ensure that any critical device or instrument used for a clinical evaluation/test during a clinical trial that provides important information about inclusion/exclusion criteria and/or safety or efficacy parameters shall be suitably calibrated and maintained to ensure that the data obtained is reliable and/or

reproducible. Documentation of equipment calibration must be retained as source documentation at the trial site.

Critical Equipment for this trial includes:

none

